First dose pre and post spirometry: All subjects will undergo spirometry before and 20 minutes after the first study drug dose as follows.

Perform baseline spirometry and measure SpO₂. Multiply the patient's best FEV₁ by 0.80 to obtain 20% fall in FEV₁ value.

Premedicate subject with 4 puffs albuterol and wait 15-30 min.

Begin study drug nebulization.

Wait for 15-30 minutes and repeat spirometry and SpO₂.

Subject is excluded from the study if SpO₂ is <89% or FEV₁ declines by 20% or greater from baseline.

Administration: Subjects will take their routine inhaled medicines followed by chest physical therapy. All subjects will then receive 2-4 puffs of albuterol metered dose inhaler 15-30 minutes before the study drug. Finally the study drug will be inhaled. All empty, unused and partially used study drug containers will be tracked by the investigators. Subjects will be required not to use any new treatments if not medically indicated during the study period.

Day 14 follow-up: Subjects will undergo spirometry and sputum collection and answer CFQ-R questionnaire. Blood draw for LFTS and electrolytes will be done if not done for clinical reasons. If subjects are discharged prior to 14 days of xylitol use, nebulizer solutions will be sent home. They will be asked to keep a log of nebulizer use and bring back empty and unused vials on follow-up visit (Day 10-15, preferably day 14). They will undergo spirometry and sputum collection and questionnaire administration on that day. If subjects don't return on this day, they will have a phone follow-up for adverse events and compliance.

Phone follow-up: Week 1, Day 90 and Day 180 after discharge: Subjects will be contacted by phone at these time points to enquire about further pulmonary exacerbations, admissions, and other AEs.

In the event of bronchospasm: Subjects will alert the nurses or study team members. Nebulized bronchodilators will be immediately administered. Once symptoms resolve, they will undergo spirometry using a portable handheld spirometer by a trained user. If the subjects dropped FEV₁ by 20% or greater from their baseline, they will not receive further study drug. However, they will remain in the study for completion of data collection.

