Endpoints: Primary outcome will be FEV₁ change from baseline. Other safety assessments include vital signs within 30 minutes after nebulization, withdrawal from the study, rescue bronchodilator use, incidence of treatment related adverse events, and laboratory tests (chemistry and liver function tests). Efficacy outcomes include difference in density of colonization per gram of sputum from baseline to day 14, time to next hospitalization, difference in CFQ-R, sputum cytokine levels and cell counts.

Adverse events such as cough, chest tightness, and headache will be scored on a visual analog scale. Other variables collected include antibiotic and other medication use during the hospitalization, demographics, organ involvement with CF, genotype data from medical records. Follow-up phone calls will be made 1 week, 3 months and 6 months

after study completion for any complications and to assess the time to next hospitalization.

Adverse events: Any untoward medical occurrence (abnormal symptom, sign or laboratory value) in a study subject that is temporally associated with the study drug will be reported as an adverse event. The event does not have to have a causal relationship with the treatment. The event will be classified by the investigator as mild, moderate or severe. The relationship of an adverse event to the study drug will be determined by the investigator to be ‘unlikely to be related, possibly related, probably related or definitely related’.

Future Use of Stored Specimens

Subjects will be asked for permission to keep any remaining unlinked sputum and blood specimens for possible use in future research studies. Samples may be shared with other investigators at other institutions. The samples will not be sold or used directly for production of any commercial product. No human genetic tests will be performed on samples. Each sample will be labeled only with a study ID to protect subject’s confidentiality.

There are no benefits to subjects in the future research use of their specimens. Reports about future research done with these samples will not be kept in their health records.

Subjects can decide if they want their samples to be used for future research or have their samples destroyed at the end of the study. A subject’s decision can be changed at any time prior to the end of the study by notifying the study investigators in writing.

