The primary outcome is FEV₁ change from baseline. To test for a difference in the mean change between the treatment group and the control group, a two-sample t-test will be conducted. To estimate the difference in the mean change, the equivalent confidence interval procedure will be used. Prior to conducting the test, normality will be assessed for each group based on normal probability plots. If gross departures from normality are observed, a Wilcoxon rank sum test will be performed instead of the t-test. (With group sample sizes of 30, the t-test is fairly robust to departures from normality.)

The same analytical approach will be used to assess differences in the group means for the following variables: the primary outcome of change in respiratory symptom score, and the efficacy outcomes of change in density of colonization (per gram of sputum),

change in sputum cytokines and cell counts, and responses to all Likert-scale questions on the CFQ-R.

To analyze group differences in the efficacy outcome of time to next exacerbation, a time-to-event analysis will be conducted. Kaplan-Meier estimates will be obtained for each survival curve (where failure is defined by exacerbation). To compare the survival distributions, a log rank test will be employed.

To compare the proportion of subjects in each group who have experienced any adverse events, Fisher's exact test will be used. Since certain subjects may experience multiple adverse events, we will also compare the incidence of adverse events in each group. For this comparison, a test will be conducted to contrast the mean number of events in each group, where the two samples of event counts are treated as arising from independent Poisson distributions. To estimate the difference in group proportions and the difference in group means, equivalent confidence interval procedures will be employed.

The preceding inferential procedures will be conducted for individual types of adverse events (e.g., cough, chest tightness, headache), as well as the aggregate of all adverse events. Fisher's exact test will also be used to compare the compliance proportion and the proportion of rescue bronchodilator use in each group.

Since this study is a randomized, controlled clinical trial, we expect the treatment group and the control group to be balanced with respect to factors that could affect the primary

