and efficacy outcomes, such as age and gender. For such variables, descriptive statistics will be compiled for each group to ensure that the randomization has been effective. If a marked difference is observed in the distribution of any variables, an analytical approach will be utilized that will allow us to control for these variables. Specifically, the t-test can be replaced with an analysis of covariance model, the log-rank test can be replaced with a Cox proportional hazards model, Fisher's exact test can be replaced with a logistic regression model, and the two-sample Poisson test can be replaced with a Poisson regression model.

All analyses will be performed by the study statistician using SAS version 9.2 (SAS Institute, NC).

Risks: Exposure to xylitol and hypertonic saline is expected to not elicit any significant symptoms other than some cough; however we recognize that there may be a possibility of bronchospasm with the hyperosmolar xylitol in a subgroup of subjects with CF who have bronchial hyperresponsiveness that was not known previously.

Blood draw and spirometry are a part of standard care and will not pose added risks.

With the admission labs that are routinely done, we will collect another red top tube for liver function tests if they were not planned. Answering questions may involve some concentration and may be boring.

Risks are minimized as follows: In the event of bronchospasm with the study drug, immediate treatment with bronchodilators is available. The subject will undergo a spirometry and if the FEV₁ has declined by 20%, the subject will be terminated from the

study. Blood draw will be performed by trained nurses or the hospital IV team with minimal discomfort. Spirometry will be done by experienced respiratory therapists. Symptom questionnaire will be administered by well-trained interviewers and will be as brief as possible.

Confidentiality: All the test results and questionnaire will be stored in the research office under lock and key with access only to the investigators. Once all testing is complete and data is entered for analysis, there will be no identifiers connecting the subject to the data. All results will be reported in summary without identifying the subjects. Blood and urine specimens will not be stored for future use.

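### Adverse events are compared as mean counts with no observation time, while the documents conflict on whether follow-up continues after a harm-related stop

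*Combined protocol and SAP*

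**What the plan says.** The Outcomes part of the statistical analysis plans two adverse-event comparisons.

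- Proportions: "To compare the proportion of subjects in each group who have experienced any adverse events, Fisher's exact test will be used".
- Counts: "a test will be conducted to contrast the mean number of events in each group", in which "the two samples of event counts are treated as arising from independent Poisson distributions".

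Both are repeated for individual event types and for the aggregate. Everyone who took one dose or more is analysed. No dose count, number of days or counting window enters either comparison. The only count regression is a fallback: "the two-sample Poisson test can be replaced with a Poisson regression model". Its trigger is baseline imbalance, with age and gender as the examples: "If a marked difference is observed in the distribution of any variables, an analytical approach will be utilized". No offset is named.

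Under Adverse events, an untoward occurrence "temporally associated with the study drug will be reported as an adverse event". Causality is not required, and no end of the reporting window is given. Later calls also ask about events. The Phone follow-up paragraph times them from discharge, and Endpoints times them from study completion.

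On what follows a stop, the first-dose spirometry rule says: "Subject is excluded from the study if SpO₂ is <89% or FEV₁ declines by 20% or greater from baseline". The bronchospasm paragraph withholds further study drug after a 20% FEV₁ fall, but says of these subjects that "they will remain in the study for completion of data collection". Study Performance and the risk-minimisation paragraph instead end participation at a 20% fall.

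**The concern.** A mean count per subject compares arms fairly when all subjects are watched for the same time. If follow-up ends at the stop, a subject who leaves after the first dose is a full subject in the denominator but can contribute events for only about 1/28 of the planned course. The stops in question are triggered by low SpO₂ or an FEV₁ fall, so the lost time would fall mainly on the arm that causes more such harm. The Risks section itself allows for bronchospasm with xylitol in some subjects.

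At stake is a central safety comparison. The Abstract lists adverse events among the primary outcomes, the group size of 30 is justified by adverse-event detection, and the count test is the only planned analysis that uses repeated events.

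**Working it through.** **The plan's own figure.** The safety sample size rests on the chance of at least one event among 30 subjects at 5% each: 1 − 0.95³⁰ = 0.785, within two points of the stated 80% (32 subjects give 1 − 0.95³² = 0.806). This point does not dispute it. The figure contains no event rate over time and no stop fraction, so it cannot size the problem. The stop fractions, stop times and event rates below are assumptions.

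**Follow-up rules side by side**

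| Place | Trigger | Follow-up afterwards |
|---|---|---|
| First dose pre and post spirometry | SpO₂ or FEV₁ after dose 1 | Excluded; later event follow-up not stated |
| In the event of bronchospasm | 20% FEV₁ fall | Drug stops, data collection continues |
| Study Performance; risk minimisation | 20% FEV₁ fall | Participation ends |

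Under the second row no observation time is lost. Under the third it is, and under the first it may be.

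**Event types that are not the stopping event (headache, for example).** Twice daily for 14 days is 28 doses. Assume a constant event rate, full follow-up in the saline arm, and a fraction s of the xylitol arm whose follow-up ends after dose 1. Then

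count ratio ÷ true rate ratio = [(1 − s) × 28 + s × 1] / 28

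- s = 5%: 26.65/28 = 0.95
- s = 10%: 25.3/28 = 0.90
- s = 20%: 22.6/28 = 0.81

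Counting by days gives the same answer for 6 stops of 30 on day 1: (24 × 14 + 6 × 1)/(30 × 14) = 342/420 = 0.81. With equal true rates the count ratio is 0.81 and the person-day ratio 1.00.

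**Aggregate, with the stop counted as one event.** Keep 30 per arm, 6 xylitol stops on day 1, none on saline, and equal background rates of λ events per subject per 14 days.

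Xylitol total = 24λ + 6(1 + λ/14); saline total = 30λ; person-days 342 and 420.

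| λ | Count ratio | Person-day ratio |
|---|---|---|
| 0.5 | 18.21/15 = 1.21 | 1.49 |
| 1 | 30.43/30 = 1.01 | 1.25 |
| 2 | 54.86/60 = 0.91 | 1.12 |
| 3 | 79.29/90 = 0.88 | 1.08 |

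The person-day ratio is the count ratio divided by 342/420. The count ratio is always the lower of the two. It falls below 1 only when λ exceeds 1/(1 − 1/14) = 1.08.

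**Aggregate, with a truly higher background rate on xylitol.** For rate ratio R and n stops, the count ratio equals 1 at λ = n / [30 − (30 − n)R − nR/14].

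- R = 1.2, n = 6: 6/0.686 = 8.75 events per subject
- R = 1.2, n = 9: 9/4.03 = 2.2
- R = 1.2, n = 3: never
- R = 1.5, n = 3, 6 or 9: never

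At R = 1.25 and s = 20% after dose 1, the count ratio without the stop event is 1.25 × 0.807 = 1.01. Counting the stop adds 0.20/λ, which gives 1.21 at λ = 1 and 1.11 at λ = 2.

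**The case against.** A reader might infer that the arm with more stops will look safer than the other arm. The documents do not support that. An FEV₁ or SpO₂ fall fits the plan's broad definition of an adverse event, so the stop can enter the count, and reversal then depends on a background rate that is nowhere given. A reader might also infer that no event can be recorded once dosing ends. The definition requires no causal link and sets no end date, and the calls continue to ask about events.

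The case for leaving the plan alone has more to it:

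- If data collection continues after every stop, the mean count over a common window is a valid as-randomised comparison. This stands, but only under one of the conflicting rules.
- Stops are not hidden. Withdrawal is a listed safety assessment, terminations and their reasons are measured, and the proportion with any event is tested. This stands too, though for a type that is not the stopping event the proportion suffers the same truncation, and no comparison of stops by arm is named.
- The Stopping criteria close recruitment after three FEV₁ falls if all are on xylitol, which makes 6 stops against 0 an extreme case. That is fair. But three stops are already 10% of 30, or 20% if they occur with 15 in the arm, and SpO₂ stops are not counted by that rule.
- The shrinkage is small beside the noise. With an assumed 60 events per arm, the 95% limits are the estimate multiplied or divided by exp(1.96 × √(2/60)) = 1.43. This is true, but a systematic shift toward safety is still worth removing when it is cheap to do so.
- A per-dose rate conditions on something that happens after randomisation and assumes a constant rate, which is doubtful if harm clusters at the first dose. This stands, and it is why the rate should accompany the mean count and not replace it.

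**Conclusion.** The concern holds conditionally. The count comparison carries no observation time, nothing elsewhere in the plan supplies it, and the documents disagree on whether follow-up ends at a harm-related stop. Where it does end, the mean count understates the event burden in the arm with more stops. For types other than the stopping event, the count ratio is 0.95, 0.90 or 0.81 of the true rate ratio for 5%, 10% or 20% stopped after the first dose in one arm and none in the other. Those figures assume a constant event rate and the earliest possible stop. For the aggregate the loss is partly offset by the stop event itself. The size in this trial cannot be fixed from the documents.

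**What to change.** 1. Reconcile the first-dose rule, the bronchospasm paragraph, Study Performance and the risk-minimisation paragraph on data collection after a stop. Which rule should govern clinically is for the investigators.
2. Define one adverse-event counting window for all dosed subjects, apply it wherever data exist, and state that the stopping event counts as an adverse event.
3. Beside the mean count, report a Poisson regression, or one robust to overdispersion, with log(days under observation) as offset. Give the rate ratio and confidence interval for each type and for the aggregate.
4. Show harm-related stops by arm next to these results. Treat any per-dose rate as a sensitivity analysis only.

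The cost is a clarification of the text and one offset term in a model the plan already names. There are limits. The rate assumes a constant hazard and does not by itself remove informative stopping, and observation time for subjects who do not return rests on the phone report.

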However, if a subject consents to future use and some of their specimens have already been used for research purposes, the information from that research may still be used.

Statistical analysis: We plan to enroll a total of 60 subjects for this study. These subjects will be randomly assigned to the treatment (xylitol) and control (saline) groups, with a goal of 30 subjects in each group. Since this is a pilot safety study, it has been primarily powered to detect common adverse events. Assuming that the likelihood of a subject experiencing an adverse event is no less than 5%, a sample size of 30 subjects ensures 80% power towards event detection [16]. (In other words, with a group sample size of 30, the probability of observing at least one adverse event in the group is at least 80%.)

Study Performance

Accrual will be assessed on a monthly basis. We will examine the number of screened subjects, those meeting eligibility criteria, the number of persons consenting to participate and the number of randomized. The rate of accrual will be tracked versus the expected number to achieve the target of 60 participants randomized.

We will also track the completion number and proportion by time. The number of study terminations and reason for termination will be measured. The subject will undergo a spirometry and if the FEV₁ has declined by 20%, the subject will be terminated from the study.

Baseline

The composition of the study sample will be described in aggregate. Comparison of randomized participants of baseline characteristics will be analyzed using 2 sample t-test,

Wilcoxon rank sum test, and analysis of variance (ANOVA) as indicated by the type and characteristics of the variable.

Outcomes

To assess the adequacy of these group sample sizes for testing a trend in efficacy, we consider the outcome of log CFU. We assume an average density of colonization of 6.5 log CFU with a SD of 1.5 log CFU among CF subjects. To detect a reduction of 1.5 log CFU in the xylitol group with 80% power, the required sample size is 17 subjects per group. (This computation is based on a two-sided, two-sample t-test conducted at the 0.05 level of significance.) Data from all patients who have received at least one dose of the drug or placebo will be analyzed. Thus, the analysis will be based on intention to treat. All tests will be two-sided, and conducted using a significance level of 0.05.

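### The test and interval for mean adverse-event counts fix the variance at the mean, with no dispersion check and no rule for counting repeat episodes

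*Combined protocol and SAP*

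**What the plan says.** All of this is in the Outcomes part of Statistical analysis unless another section is named.

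- **Reason for counting.** "Since certain subjects may experience multiple adverse events, we will also compare the incidence of adverse events in each group".
- **Method.** Mean counts are contrasted in a test "where the two samples of event counts are treated as arising from independent Poisson distributions". The form of the test (z, exact conditional, likelihood ratio) is not named.
- **Interval.** For "the difference in group means, equivalent confidence interval procedures will be employed". The interval therefore rests on the same variance as the test.
- **Scope.** The procedures are "conducted for individual types of adverse events (e.g., cough, chest tightness, headache), as well as the aggregate of all adverse events".
- **Alternative.** If baseline variables differ markedly between the arms, "the two-sample Poisson test can be replaced with a Poisson regression model". Baseline imbalance is the only trigger. No scale factor, robust variance or exposure offset is mentioned.
- **Level and size.** "All tests will be two-sided, and conducted using a significance level of 0.05", "with a goal of 30 subjects in each group".
- **Recording.** Under Endpoints, "Adverse events such as cough, chest tightness, and headache will be scored on a visual analog scale". Nothing says whether a second episode of the same type in one subject adds to the count. A separate data and safety monitoring plan is cited under Safety Monitoring but was not available.
- **Companion test.** Fisher's exact test compares the proportions of subjects with any event, overall and by type.

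**The concern.** A Poisson test takes its standard error from the mean alone. If subjects differ in their underlying rate and repeats are counted, the true variance exceeds the mean. The test then rejects too often and the interval is too narrow. If each type is counted at most once per subject, the counts are 0 or 1 and the variance is below the mean. A z or exact test then usually rejects too seldom and the interval is too wide.

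The plan gives reasons to expect a departure. It expects repeat events in some subjects. The Risks section foresees a subgroup with unrecognised bronchial hyperresponsiveness. Exposure also varies: a subject may leave after the first dose, and everyone with at least one dose is analysed. The same section checks normality before the t-test and names a substitute, but the count test has no such safeguard.

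The count comparison is the only planned analysis that uses more than one event per subject. A few subjects with many events could make the arms look different in either direction. For a type counted once, the count test could miss a difference that Fisher's test shows on the same data.

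**Working it through.** **Inputs from the documents.** 30 per arm, two-sided 0.05, Poisson variance. The only event frequency given is a per-subject probability of at least 5%, used in the sample-size statement. There it gives 1 − 0.95³⁰ = 78.5%, against a stated 80%; that figure does not bear on the count test.

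**Assumed, because the documents give nothing.** Mean count per subject μ, variance-to-mean ratio φ, and the share of subjects affected under once-only counting.

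**Tests.** With arm totals a and b, z = |a − b| / √(a + b). The exact conditional test treats a as binomial(a + b, ½) and doubles the smaller tail.

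**Step 1: large-sample size.** The assumed standard error of the difference in means is √(2μ/30) and the true one is √(2φμ/30). The size is therefore about 2[1 − Φ(1.96/√φ)], which is 8.0%, 11.0% and 16.6% at φ = 1.25, 1.5 and 2. For example, at μ = 1 and φ = 2 the assumed standard error is √(2/30) = 0.258 and the true one is √(4/30) = 0.365.

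**Step 2: exact enumeration of arm totals.** Gamma-mixed Poisson counts, μ = 0.5 to 4. The row φ = 1 reproduces the plan's nominal level for the z-test.

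| φ | z-test size | exact test size | coverage of nominal 95% Wald interval |
|---|---|---|---|
| 1 | 4.9–5.2% | 3.1–4.3% | 95% |
| 1.25 | 7.9–8.1% | 5.3–7.0% | 92% |
| 1.5 | 10.8–11.1% | 7.7–9.8% | 89% |
| 2 | 16.4–16.6% | 12.5–15.2% | 83–84% |

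**Step 3: what would produce such ratios.** If subjects' rates have coefficient of variation c, then φ = 1 + c²μ. With c = 0.5, φ is 1.25, 1.5 and 2 at μ = 1, 2 and 4, so under this model the top of the range needs about four events per subject. As a second example, suppose 20% of subjects average 2 events and the rest 0.5. The mean is 0.8 × 0.5 + 0.2 × 2 = 0.8, the variance of the rates is 0.8 × 0.2 × 1.5² = 0.36, and φ = 1 + 0.36/0.8 = 1.45. The z-test then runs at 10.2% and the exact test at 8.2%.

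**Step 4: each type counted at most once.** With event probability p, φ = 1 − p.

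| p | z-test | exact test | Fisher |
|---|---|---|---|
| 5% | 2.7% | 0.15% | 0.15% |
| 10% | 3.8% | 0.9% | 0.9% |
| 20% | 2.5% | 1.2% | 2.2% |
| 30% | 2.0% | 1.0% | 2.6% |
| 50% | 0.7% | 0.3% | 2.7% |
| 60% | 0.2% | 0.1% | 2.6% |

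For a true 30% against 60%, power is 40% (z) or 28% (exact), against 56% for Fisher.

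**Step 5: rare but over-dispersed events.** At μ = 0.05 and φ = 1.5 and 2, the z-test runs at 6.5% and 9.6%, and the exact test at 1.4% and 3.1%.

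**Step 6: the observed-variance alternative.** A Welch test on per-subject counts has a simulated size of about 4–5% for μ = 0.5 to 4 and φ = 1 to 2. For 0/1 counts at p = 20–50% its size is 4.9–5.2%. With sparse over-dispersed counts (φ from 1.25 to 2) it becomes conservative: 1.5% down to 0.5% at μ = 0.05.

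**The case against.** The strongest reply is that no trial figure supports any of these sizes. The mean, the dispersion and the frequency are all assumed, and the error can go either way. That stands: the figures show what the plan leaves open, not what will happen.

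It is also fair that Fisher's test, already planned overall and by type, does not rest on the Poisson assumption. Under once-only counting it uses the same data, so the power lost there is lost in a redundant test. That limits the consequence. It does not help the analysis of repeat events, for which Fisher's test is no substitute.

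Three stronger readings are tempting, and the documents do not support them.

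- *The count test will be liberal in this trial.* This needs repeats to be counted and the variance to exceed the mean, and neither is stated. At φ = 1.25 and a mean of 0.5, the exact test runs at 5.3%, close to nominal.
- *Once-only counting always gives 0.3–2.5%.* That range holds for 20–50% of subjects affected. At 10% the z-test runs at 3.8%, and at 60% both tests fall below 0.3%. A likelihood-ratio version, which the plan does not rule out, is liberal at 5–10% affected (8.3–7.4%).
- *Rare events are safe because the test is conservative there.* This is true for Poisson or 0/1 counts with the z or exact test. It fails for the z-test once rare events cluster in a few subjects (Step 5).

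**Conclusion.** The concern holds as a conditional one. The plan fixes the variance of adverse-event counts at their mean in the test, the interval and the fallback model, and it has no check on that assumption. With 30 per arm, at least 0.5 events per subject and a variance-to-mean ratio of 1.25 to 2 (both assumed), the nominal 5% test runs at about 8–17% (z) or 5–15% (exact), and the 95% Wald interval covers about 92–83%. With once-only counting and 20–50% of subjects affected (assumed), it runs at 2.5–0.7% (z) or 1.2–0.3% (exact). For rarer events the result depends on the unnamed form of the test and on the dispersion.

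The point is worth considering but not critical. Endpoints makes FEV₁ change the primary outcome and lists adverse events among the other safety assessments, although the Abstract groups them with the primary safety outcomes. The FEV₁ analysis and Fisher's test do not use the Poisson variance, and no stopping rule uses the count p-value.

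**What to change.** 1. State whether repeat episodes of one type in a subject count as separate events.
2. For all events together and for non-sparse types, keep the difference in mean events per subject. Base its test and 95% interval on the observed between-subject variance in each arm, for example by Welch's method, and report the Pearson dispersion.
3. For sparse types and for types counted once per subject, rely on the Fisher's exact test already planned. The statistician should fix the cut-off for sparse in advance, because Welch is itself conservative there.
4. If covariate adjustment is needed, replace plain Poisson regression by a Pearson-scaled (quasi-Poisson) or robust-variance model, or by a negative binomial model if counts are over-dispersed. State that it estimates a rate ratio, not a difference in means.

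**Cost.** A few sentences in the analysis plan and no new data. If counts are truly Poisson, power falls by 1–2 points (about 75% to 73–74% for means 1 against 1.8; about 76% to 75% for 2 against 3.1) and the interval is about 2% wider. If counts are over-dispersed, intervals widen as they should, by factors of about 1.13, 1.24 and 1.43 at ratios 1.25, 1.5 and 2.
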